During the study, in the case of Grade ≥ 3 immune-related pneumonitis, Grade ≥ 3 TBIL elevation (recurrent), Grade 4 ALT/AST elevation (recurrent), other Grade 4 immune-related toxicities (except for hypothyroidism), Grade 4 injection reactions, or the interruption of SHR-1210 administration for more than 12 weeks due to immune-related toxicity but the toxicity is still unable to return to Grade ≤ 1 or baseline levels (subjects with baseline abnormality), SHR-1210 should be permanently discontinued.

After discontinuation of SHR-1210 treatment, subjects may continue to receive apatinib monotherapy after toxicity recovery if the investigator judges that the subjects can benefit from the apatinib monotherapy, until an event meeting the criteria for discontinuation as specified in the protocol occurs.

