8.7 Immune-Related Adverse Events (irAEs)

Immune-related adverse events (irAEs) are clinically significant side effects that are consistent with the immunological mechanisms of the study drug. irAEs require further serological, immunological and pathological (biopsy) data to support its diagnosis. Also, tumors, infections, metabolism, toxins, or other pathogenic factors must be ruled out.

Management principles for immune-related adverse events (see Appendix IV for details):

● Immune-related pneumonitis

In the clinical study of SHR-1210, the monitoring of signs and symptoms of immune-related pneumonia, such as cough and chest discomfort, in the subjects will be strengthened. Examinations will be carried out via imaging tests (e.g., X-ray), and a high-dose hormone therapy will be given to subjects with a Grade 2 or greater event. Subjects with a Grade 2 event can interrupt SHR-1210 and be treated, but subjects with a Grade 3 or 4 event should permanently discontinue SHR-1210.

- **Immune-related enteritis**

In the clinical study of SHR-1210, the monitoring of signs and symptoms of immune-related enteritis, such as abdominal pain, diarrhea, and hematochezia, in the subjects will be strengthened. A high-dose hormone therapy will be given to subjects with a Grade 2 or greater event. Subjects with a Grade 2 or 3 event can interrupt SHR-1210 and be treated, but subjects with a Grade 4 event should permanently discontinue SHR-1210.

- **Immune-related hepatitis**

In the clinical study of SHR-1210, the monitoring of signs and symptoms of immune-related hepatitis, such as liver discomfort and abnormally increased transaminase, in the subjects will be strengthened. A high-dose hormone therapy will be given to subjects with a Grade 2 or greater event. Subjects with a Grade 2 event can interrupt SHR-1210 and be treated, but subjects with a Grade 3 or 4 event should permanently discontinue SHR-1210.

- **Immune-related thyroid dysfunction**

Thyroid dysfunction can occur at any time during the study. Therefore, in clinical studies of SHR-1210, thyroid functions of subjects will be regularly examined to closely monitor the clinical symptoms of thyroid dysfunction. After the occurrence of immune-related hyperthyroidism, the subject should be given a high dose of cortisone/prednisone. Hormone replacement therapy is used for the treatment of hypothyroidism, but glucocorticoids are not applicable.

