In the clinical study of SHR-1210, the monitoring of signs and symptoms of immune-related thyroid dysfunction in the subjects will be strengthened. A high-dose hormone therapy will be given to subjects with a Grade 3 or greater event, but subjects with a Grade 4 event should permanently discontinue SHR-1210.

- **Immune-related nephritis and renal failure**

In the clinical study of SHR-1210, the monitoring of signs and symptoms of immune-related nephritis in the subjects will be strengthened. A high-dose hormone therapy will be given to subjects with a Grade 2 or greater event. Subjects with a Grade 2 event can interrupt SHR-1210 and be treated, but subjects with a Grade 3 or 4 event should permanently discontinue SHR-1210.

● Immune-related hypophysitis

In the clinical study of SHR-1210, the monitoring of signs and symptoms of immune-related hypophysitis in the subjects will be strengthened. A high-dose hormone therapy will be given to subjects with a Grade 2 or greater event. Subjects with a Grade 2 or 3 event can interrupt SHR-1210 and be treated, but subjects with a Grade 4 event should permanently discontinue SHR-1210.

● Other immune-related adverse reactions

In principle, interruption of SHR-1210 is preferred based on the severity of the adverse reaction. The study treatment can be considered to resume when AE returns to Grade ≤ 1 . The study treatment should be permanently discontinued if severe (Grade 3) or life-threatening (Grade 4) adverse reactions occur.

The treatment of immune-related adverse reactions should be based on the medical practice and guidelines of the study center. The treatment recommendations for irAEs are shown in Table 8-2 for reference.

Table 8-2. Treatment recommendations for irAEs related to SHR-1210 for injection

CTCAE Grade	Clinical Management*	SHR-1210 Treatment
Grade 1 (mild)	
 - Close observation, especially for diarrhea • Supportive care 	Continue
Grade 2 (moderate)	
 - Closely monitoring • Supportive care • Local application of steroids, such as for dermatitis/colitis, etc. 
Symptoms persist for ≥ 7 days, start 1 mg/kg of prednisone or equivalent
 
Symptoms are aggravated, give intravenous or oral administration of 1 mg/kg prednisone
	Interrupt, resume when recovers to Grade ≤ 1
Grade ≥ 3 (severe)*	-2 mg/kg of prednisone or equivalent	Permanent discontinuation

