9 MANAGEMENT OF ADVERSE EVENTS

9.1 Immune-Related Adverse Events (irAEs)

Immune-related adverse events (irAEs) are clinically significant side effects that are consistent with the immunological mechanisms of the study drug. irAEs require further serological, immunological and pathological (biopsy) data to support its diagnosis. Also, tumors, infections, metabolism, toxins, or other pathogenic factors must be ruled out.

Management principles for immune-related adverse events (see Appendix IV for details):

The treatment of immune-related adverse reactions should be based on the medical practice and guidelines of the study center. The treatment recommendations for irAEs are as follows. The details are shown in Appendix IV for reference.

Subjects using hormones should pay attention to calcium and vitamin D3 supplement, acid suppression, and protection of gastric mucosa.

● **Immune-related pneumonitis**

In the clinical study of SHR-1210, the monitoring of signs and symptoms of immune-related pneumonia, such as cough and chest discomfort, in the subjects will be strengthened. A high-dose hormone therapy will be given to subjects with a Grade 2 or greater event confirmed by chest CT. Subjects with Grade 2 immune-related pneumonitis can interrupt SHR-1210 and be treated, but subjects with a Grade 3 or 4 immune-related pneumonitis should permanently discontinue SHR-1210. Consultation with the Department of Respiration is recommended.

For specific operations, refer to the followings:

Grade 2 event: 1 mg/kg/day of methylprednisolone or equivalent given via intravenous or oral administration. The changes in CT should be closely monitored. After the event recovers to Grade 1, oral administration of 0.5 mg/kg/day of prednisone can be continued for 2 weeks, then the dose of prednisone should be reduced by 5 mg/week until drug discontinuation.

Grade 3 event: 2-4 mg/kg/day of methylprednisolone or equivalent given via intravenous injection. The changes in CT should be closely monitored. After the event recovers to Grade 1, the dose of methylprednisolone should be reduced by 50% every 3 days. Oral administration of 0.5 mg/kg/day of prednisone can be continued for 2 weeks, then the dose of prednisone should be reduced by 5 mg/week until drug discontinuation.

If the hormone therapy does not improve or deteriorate the condition after 3-5 days, a combination therapy with immunosuppressants may be used for the treatment after discussion with the sponsor.

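### The protocol contradicts itself on immune-related thyroid dysfunction: whether Grade 4 hypothyroidism ends SHR-1210, and from which grade hyperthyroidism receives high-dose steroid

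*Protocol*

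**What the plan says.** Three parts of the protocol set rules for thyroid events.

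- **Section 8.7, thyroid bullet, first paragraph.** For hyperthyroidism: "After the occurrence of immune-related hyperthyroidism, the subject should be given a high dose of cortisone/prednisone". For hypothyroidism: "Hormone replacement therapy is used for the treatment of hypothyroidism, but glucocorticoids are not applicable". Neither sentence carries a grade.
- **Section 8.7, thyroid bullet, second paragraph.** For thyroid dysfunction as a whole: "A high-dose hormone therapy will be given to subjects with a Grade 3 or greater event". On stopping: "subjects with a Grade 4 event should permanently discontinue SHR-1210". Neither clause separates the two conditions.
- **Section 9.1** repeats both paragraphs.
- **Section 6.4** lists the reasons for permanently discontinuing SHR-1210. One item reads "other Grade 4 immune-related toxicities (except for hypothyroidism", with the bracket closing after that word.
- **Table 8-2 (Section 8.7)** gives generic recommendations for immune-related events. Its row for Grade 3 or greater has "2 mg/kg of prednisone or equivalent" and permanent discontinuation. The row is marked with an asterisk, and the footnote relaxes it for Grade 3 local skin and endocrine disorders.

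Section 8.7 also says that treatment should follow the study center's practice and guidelines, and offers Table 8-2 for reference. Section 9.1 defers to study-center practice in the same way. Both sections point to Appendix IV for details.

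**The concern.** An investigator with a thyroid event has to decide two things: whether to give high-dose glucocorticoid, and whether SHR-1210 ends. For some combinations of condition and grade, the protocol gives two answers to one of these questions. A site that follows one sentence departs from the other, and two sites can treat the same event differently while each can cite the protocol.

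The main stake is patient management: high-dose steroid given or withheld, and immunotherapy ended or continued, according to which paragraph is consulted. The secondary stake is the safety reporting. Protocol Section 13.4.4 summarizes thyroid dysfunction among the immune-related events, and SAP Section 5.4.3 tabulates adverse events leading to discontinuation of SHR-1210. Part of what those tables show for thyroid events would reflect the choice of paragraph.

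**Working it through.** **Step 1: set the rules side by side.** The columns show the condition-specific steroid sentence (8.7/9.1), the steroid sentence by grade (8.7/9.1), the SHR-1210 stop in the thyroid paragraph (8.7/9.1), and the grade-based permanent stops in 6.4.

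| Event | Steroid, by condition | Steroid, by grade | Stop, 8.7/9.1 | Stop, 6.4 |
|---|---|---|---|---|
| Hyperthyroidism, Grade 1-2 | High dose | Below threshold | None | None |
| Hyperthyroidism, Grade 3 | High dose | High dose | None | None |
| Hyperthyroidism, Grade 4 | High dose | High dose | Permanent | Permanent |
| Hypothyroidism, Grade 1-2 | No glucocorticoid | Below threshold | None | None |
| Hypothyroidism, Grade 3 | No glucocorticoid | High-dose hormone | None | None |
| Hypothyroidism, Grade 4 | No glucocorticoid | High-dose hormone | Permanent | Excepted |

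**Step 2: read off the conflicts.**

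1. *Grade 4 hypothyroidism, stopping.* Sections 8.7 and 9.1 end SHR-1210; Section 6.4 excepts the event by name. This needs no interpretation. The Table 8-2 footnote does not settle it, because it covers Grade 3 only.
2. *Grade 1-2 hyperthyroidism, steroid.* The ungraded sentence calls for a high dose. The graded sentence starts high-dose therapy at Grade 3. The second does not expressly forbid steroid below Grade 3, but a threshold has no function if every grade already qualifies.
3. *Grade 3-4 hypothyroidism, steroid.* Glucocorticoids are ruled out in one sentence, and hypothyroidism is not excluded from the next. This is a conflict only if hormone therapy means glucocorticoid. Elsewhere it does: the specific instructions that follow the same phrase for pneumonitis in 9.1 begin "Grade 2 event: 1 mg/kg/day of methylprednisolone or equivalent given via intravenous or oral administration". Table 8-2 names prednisone outright and has no hypothyroidism exclusion.

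**Step 3: size.** The inputs are the tables in Protocol Section 1.7.1, from the three phase I studies of SHR-1210 in China.

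- *Denominator.* The table heads print N = 67, the number with any adverse event, but the percentages use 87. For hypothyroidism, 8/87 = 9.2%, as printed, whereas 8/67 = 11.9%.
- *Treatment-related hyperthyroidism:* 1/87 = 1.1%, as printed. Projected to Stage II: 174 × 1/87 = 2.
- *Grade 3 or greater hypothyroidism:* 1/87 = 1.1%, also 174 × 1/87 = 2. This comes from the table of all Grade 3 or greater events. The highlighting that marks related events is not visible, so relatedness is unknown.
- *Uncertainty.* The exact 95% interval for 1/87 is 0.03% to 6.2%. Times 174, this is 0.05 to 10.9, so roughly 0 to 11 subjects for each event.
- *Grade 4* is not reported separately, so the direct conflict (item 1) has no documented case.

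**The case against.** The strongest reply has four parts.

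- **Site practice governs.** Sections 8.7 and 9.1 defer to the study center's guidelines, and Table 8-2 is for reference. This softens the steroid conflicts. It does not remove the stopping conflict, because 6.4 and 8.7 both phrase the stop as something that should be done permanently.
- **Appendix IV may settle it.** Its endocrine flow chart is not shown, so grade-specific rules there cannot be checked. Even so, a figure would not remove contradictory sentences from the body.
- **The hypothyroidism steroid conflict can be read away.** The specific exclusion may be taken to limit the general Grade 3 sentence. The same bullet also uses hormone for thyroid replacement. Both readings are fair, which is why this limb is the weakest. Items 1 and 2 do not depend on it.
- **The numbers are small.** This stands.

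A reader might also infer that Table 8-2 and its footnote contradict each other on Grade 3 endocrine events. They do not. The asterisk ties the footnote to that row as an exception, and neither the thyroid paragraph nor the 6.4 list contains a grade-based permanent stop for Grade 3 thyroid events.

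**Conclusion.** The inconsistency is real and lies in the current text. It is direct for stopping SHR-1210 at Grade 4 hypothyroidism, clear enough for the steroid threshold in hyperthyroidism, and arguable for steroid use in Grade 3-4 hypothyroidism. It deserves correction because it bears on patient management, but its reach is narrow: about 2 of 174 subjects with hyperthyroidism and about 2 with Grade 3 or greater hypothyroidism. These figures assume that monotherapy rates from mixed tumors and doses carry over to the combination. They may not: Section 9.3 itself links anti-angiogenic drugs to hypothyroidism.

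Two larger readings are tempting.

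- *That patients with the commonest endocrine event are broadly affected.* Hypothyroidism was that event, and 174 × 8/87 = 16. But at Grade 1-2 the thyroid paragraphs and 6.4 agree, so most of those 16 would meet none of the three conflicts. Only the generic Grade 2 row of Table 8-2, which suggests prednisone for symptoms lasting at least 7 days, reaches lower. That row is for reference, and the documents give no count for it.
- *That DoR or PFS would shift.* Nothing shows this. SAP Section 4.1.6 counts progression whether or not treatment continues, Protocol Section 6.4 allows apatinib alone after SHR-1210 stops, and few subjects could reach a stopping conflict.

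**What to change.** Reconcile four places: the permanent-discontinuation list in Section 6.4, the thyroid paragraphs of Sections 8.7 and 9.1, and Table 8-2 with its footnote. Treat hyperthyroidism and hypothyroidism separately, and give each one steroid rule and one SHR-1210 rule per grade. Where hormone therapy is meant, say whether it is glucocorticoid or thyroid replacement. Check the endocrine chart in Appendix IV against the result. Which rule applies at each grade is for the sponsor and its clinicians; this review takes no position on it.

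The cost is protocol wording only, with no change to sample size, endpoints or analyses. If subjects have already been treated under the conflicting text, the clinical study report should say which rule sites applied to thyroid events.

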9 MANAGEMENT OF ADVERSE EVENTS

9.1 Immune-Related Adverse Events (irAEs)

Immune-related adverse events (irAEs) are clinically significant side effects that are consistent with the immunological mechanisms of the study drug. irAEs require further serological, immunological and pathological (biopsy) data to support its diagnosis. Also, tumors, infections, metabolism, toxins, or other pathogenic factors must be ruled out.

Management principles for immune-related adverse events (see Appendix IV for details):

The treatment of immune-related adverse reactions should be based on the medical practice and guidelines of the study center. The treatment recommendations for irAEs are as follows. The details are shown in Appendix IV for reference.

Subjects using hormones should pay attention to calcium and vitamin D3 supplement, acid suppression, and protection of gastric mucosa.

● **Immune-related pneumonitis**

In the clinical study of SHR-1210, the monitoring of signs and symptoms of immune-related pneumonia, such as cough and chest discomfort, in the subjects will be strengthened. A high-dose hormone therapy will be given to subjects with a Grade 2 or greater event confirmed by chest CT. Subjects with Grade 2 immune-related pneumonitis can interrupt SHR-1210 and be treated, but subjects with a Grade 3 or 4 immune-related pneumonitis should permanently discontinue SHR-1210. Consultation with the Department of Respiration is recommended.

For specific operations, refer to the followings:

Grade 2 event: 1 mg/kg/day of methylprednisolone or equivalent given via intravenous or oral administration. The changes in CT should be closely monitored. After the event recovers to Grade 1, oral administration of 0.5 mg/kg/day of prednisone can be continued for 2 weeks, then the dose of prednisone should be reduced by 5 mg/week until drug discontinuation.

Grade 3 event: 2-4 mg/kg/day of methylprednisolone or equivalent given via intravenous injection. The changes in CT should be closely monitored. After the event recovers to Grade 1, the dose of methylprednisolone should be reduced by 50% every 3 days. Oral administration of 0.5 mg/kg/day of prednisone can be continued for 2 weeks, then the dose of prednisone should be reduced by 5 mg/week until drug discontinuation.

If the hormone therapy does not improve or deteriorate the condition after 3-5 days, a combination therapy with immunosuppressants may be used for the treatment after discussion with the sponsor.

● Immune-related hepatitis

In the clinical study of SHR-1210, the monitoring of signs and symptoms of immune-related hepatitis, such as liver discomfort and abnormally increased transaminase, in the subjects will be strengthened. A high-dose hormone therapy will be given to subjects with a Grade 2 or greater event. For specific operations, refer to the followings:

Grade 2 hepatitis: 0.5-1 mg/kg/day of methylprednisolone or equivalent given via intravenous or oral administration. The changes in liver function parameters should be closely monitored. After the event recovers to Grade 1, the dose of hormone should be slowly reduced in a period no less than 1 month.

Grade 3 event: 1-2 mg/kg/day of methylprednisolone or equivalent given via intravenous or oral administration. The changes in liver function parameters should be closely monitored. After the hepatitis recovers to Grade 1, the dose of hormone should be slowly reduced in a period no less than 1 month.

If the hormone therapy does not improve or deteriorate the condition after 3-5 days, a combination therapy with immunosuppressants may be used for the treatment after discussion with the sponsor.

● Immune-related enteritis

In the clinical study of SHR-1210, the monitoring of signs and symptoms of immune-related enteritis, such as abdominal pain, diarrhea, and hematochezia, in the subjects will be strengthened. A high-dose hormone therapy will be given to subjects with a Grade 2 or greater event. Subjects with Grade 2 or 3 immune-related enteritis can interrupt SHR-1210 and be treated, but subjects with Grade 4 immune-related enteritis should permanently discontinue SHR-1210.

● Immune-related thyroid dysfunction

Thyroid dysfunction can occur at any time during the study. Therefore, in clinical studies of SHR-1210, thyroid functions of subjects will be regularly examined to closely monitor the clinical symptoms of thyroid dysfunction. After the occurrence of immune-related hyperthyroidism, the subject should be given a high dose of cortisone/prednisone. Hormone replacement therapy is used for the treatment of hypothyroidism, but glucocorticoids are not applicable.

In the clinical study of SHR-1210, the monitoring of signs and symptoms of immune-related thyroid dysfunction in the subjects will be strengthened. A high-dose hormone therapy will be given to subjects with a Grade 3 or greater event, but subjects with a Grade 4 event should permanently discontinue SHR-1210.

● Immune-related nephritis and renal failure

In the clinical study of SHR-1210, the monitoring of signs and symptoms of immune-related nephritis in the subjects will be strengthened. A high-dose hormone therapy will be given to subjects with a Grade 2 or greater event. Subjects with a Grade 2 event can interrupt SHR-1210 and be treated, but subjects with a Grade 3 or 4 event should permanently discontinue SHR-1210.

● Immune-related hypophysitis

In the clinical study of SHR-1210, the monitoring of signs and symptoms of immune-related hypophysitis in the subjects will be strengthened. A high-dose hormone therapy will be given to subjects with a Grade 2 or greater event. Subjects with a Grade 2 or 3 event can interrupt SHR-1210 and be treated, but subjects with a Grade 4 event should permanently discontinue SHR-1210.

● Other immune-related adverse reactions

In principle, interruption of SHR-1210 is preferred based on the severity of the adverse reaction. The study treatment can be considered to resume when AE returns to Grade ≤ 1 . The study treatment should be permanently discontinued if severe (Grade 3) or life-threatening (Grade 4) adverse reactions occur.

9.2 Infusion Reactions

As a fully humanized monoclonal antibody, SHR-1210 poses relatively lower risks of infusion reactions and prophylactic is therefore not required. Once an infusion reaction occurs, the infusion should be slowed or interrupted accordingly, and a supportive treatment should be given. Also, prophylactics should be given before further administrations. For acute infusion reactions (including cytokine release syndrome, angioedema, anaphylactic shock, allergic reactions, please refer to terms and criteria of NCI CTC AE v4.03), their relevant symptoms and signs usually occur during drug infusion or shortly after infusion, and usually disappear within 24 h after the infusion is completed. The signs and symptoms include: allergic reaction/hypersensitivity reaction (including drug-induced fever), coughing, chills, rigor, dizziness, headache, fatigue (weakness, somnolence), rash/peeling skin, pruritus/itching, arthralgia, myalgia, hypotension/hypertension, nausea, vomiting, diaphoresis, tachycardia, cancer pain, urticaria, dyspnea (shortness of breath), or bronchospasms. Any Grade 3 or 4 infusion reactions must be reported to the sponsor within 24 hours, and should be reported as SAEs if the criteria for SAE are met.

Management of allergic reactions should be based on the medical practice and guidelines of the study center. The treatment recommendations for infusion reactions are shown below for reference.

Table 9-1. Treatment recommendations for infusion reactions

CTCAE Grade	Clinical Symptoms	Clinical Management	SHR-1210 Treatment
Grade 1 (mild)	Mild and transient reactions;	Bedside observation and close monitoring until recovery. (Prophylactics are recommended for subsequent infusion: diphenhydramine 50 mg or equivalent, and/or acetaminophen 325-1000 mg, at least 30 minutes prior to SHR-1210 administration)	Continue
Grade 2 (moderate)	Moderate reactions requiring treatment or interruption; rapidly resolve after symptomatic treatment (such as antihistamines, non-steroidal antiphlogistics, anesthetics, bronchodilators, intravenous fluids, etc.)	Intravenous drip of normal saline, 50 mg of diphenhydramine IV or equivalent and/or 325-1000 mg of acetaminophen; Bedside observation and close monitoring until recovery. Corticosteroids or bronchodilators can be considered based on clinical needs; The amount of study drug infused should be recorded in the original medical record; Prophylactics are recommended for subsequent infusion: diphenhydramine 50 mg or equivalent, and/or acetaminophen 325-1000 mg, at least 30 minutes prior to SHR-1210 administration. Use corticosteroids (equivalent to 25 mg of hydrocortisone) when necessary.	Interrupt. Re-administer at 50% of the initial rate after symptoms resolve. If no reaction occurs within 30 min, restore the original infusion rate (100%). Closely monitor. If the symptoms recur, the administration of the current SHR-1210 dose will be discontinued.
Grade \geq 3 (severe)	Grade 3: Severe reactions with no rapid resolution after intervention and/or treatment interruption; symptom recurrence after resolution; sequelae requiring hospitalization. Grade 4: life-threatening	Immediately discontinue SHR-1210; Administer normal saline by intravenous infusion. 
 Bronchodilators are recommended: 0.2-1 mg of subcutaneous 1:1000 adrenaline injection or slow intravenous injection of 1:10000 adrenaline solution 0.1-0.25 mg, and/or intravenous diphenhydramine 50 mg plus methylprednisolone 100 mg or equivalent if necessary; Based on the guidelines for anaphylaxis of the study center; Bedside observation and close monitoring until recovery.	Permanently discontinue.

